9.4.2 ANALYSIS OF THE PRIMARY EFFICACY ENDPOINT(S)

Mann-Whitney U tests will be used to test for differences in peak YFV titer between the US and Uganda. Analyses will be stratified by gender to investigate if gender has a major impact on the observed differences. No imputation will be conducted if there is missing data.

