4 STUDY DESIGN

4.1 OVERALL DESIGN

The primary aim of this study is to determine the difference between antibody titers in the two study groups and study the relationship between endemic infections, IA, the FRCn, and CD4 and CD8 T cell subsets and the magnitude and durability of neutralizing antibody response to YFV in a cohort shown to have elevated IA, a damaged FRCn, and pan T cell depletion and a cohort that does not. This is a single arm, open-label, two cohort study of healthy adults in Kampala, Uganda and in Minnesota, USA. The cohort in Uganda will be 30 adults (15 men and 15 women) and the cohort in Minnesota will be 16 adults (8 men and 8 women). Everyone will be screened to ensure there are no contraindications to receiving YFV (e.g., immunosuppression) or the planned procedures. The inclusion and exclusion criteria are discussed in detail in the protocol that is included in the appendix. Participants will have an inguinal LN biopsy and leukapheresis prior to YFV and another LN biopsy 3 weeks after the vaccine administration. The vaccine will be given in the contralateral thigh from the first LN biopsy so that the second biopsy will be from a draining LN. PBMC and plasma will be collected at regular intervals over the 18-month follow-up period. Leukapheresis will be done again at the month 6 visit.

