9.2 SAMPLE SIZE DETERMINATION

We will enroll 30 individuals from Uganda and 16 individuals from the US. With this sample size our study will have more than adequate power to test our primary aim, differences in peak antibody titers between countries. Assuming yellow fever antibody titers show a similar range as in our previous studies (a standard deviation of 1 log) for both populations we have over 85% power to detect a difference in peak antibody titers of 1 log, with a two-sided test with alpha level of 0.05. This calculation is based on comparison to a T distribution with 43 degrees of freedom.

Since, in fact, we will be using a Mann-Whitney U test for this comparison we also illustrate that this sample size is sufficient using power simulations. For all simulations we assume that the Ugandan population will have a mean of 7.89 log titers and approximate standard deviation of 1 and the Minnesota population has a mean of 8.89 and an approximate standard deviation of 1. One thousand iterations were conducted for each simulation scenario. As is illustrated in the table below we will have over 84% power for a variety of distributional assumptions

Distribution	Uganda parameters	MN parameters	Power
Normal	$\mu=7.89, \sigma=1$	$\mu=8.89, \sigma=1$	0.871
Gamma	$k=62.25, \theta=0.13$	$k=79.03, \theta=0.11$	0.874
T + shift	$v= 20, \text{shift}=7.89$	$v= 20, \text{shift}= 8.89$	0.841

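### The gender-stratified look at peak titer includes no country-by-gender contrast, so it cannot answer the question it is set

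*Combined protocol and SAP*

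**What the plan says.** The primary analysis in Section 9.4.2 is stated as follows: "Mann-Whitney U tests will be used to test for differences in peak YFV titer between the US and Uganda". The next sentence reads: "Analyses will be stratified by gender to investigate if gender has a major impact on the observed differences". The section does not say whether stratified means a separate test in each gender or one combined test with gender as a stratum. It gives no significance level for the strata, no stratum estimates or intervals, and no rule for what counts as a major impact.

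Section 4.1 fixes the stratum sizes: Uganda has 15 men and 15 women, Minnesota 8 men and 8 women. Section 9.2 (Sample Size Determination) powers the pooled comparison only. It claims "over 85% power to detect a difference in peak antibody titers of 1 log, with a two-sided test with alpha level of 0.05" for 30 versus 16, with an SD of 1 log in each population.

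Elsewhere, gender enters only as an additive predictor: in the secondary models of Section 9.4.3, in the exploratory models of Section 9.4.9, and alongside the further clinical factors of Section 9.4.7.

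**The concern.** Whether gender has an impact on the country difference is a question of effect modification: is the Minnesota-minus-Uganda difference in men the same as in women? Two within-gender p-values do not test that. Their disagreement mostly reflects how small each stratum is. An additive gender term does not test it either, because it adjusts for gender while assuming one common country effect.

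The plan already uses the right structure for a parallel question. In Section 9.4.3 it compares antibody decay between countries through a time-by-country interaction. The gender question for peak titer has no such term.

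At stake is the reading of the gender result. If men reach significance and women do not, or the reverse, a reader may take this as a finding about sex when it is what chance produces in strata of this size.

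**Working it through.** **Inputs.** Per gender 15 Uganda and 8 Minnesota (Section 4.1). Country difference 1 log, SD 1 log, two-sided alpha 0.05 (Section 9.2). Mann-Whitney test (Section 9.4.2). Section 9.4.2 does not impute and no dropout allowance is stated, so 15 versus 8 is the most each stratum can have.

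**Step 1. Reproduce the plan's power.** SE = √(1/30 + 1/16) = 0.310 log, so the noncentrality is 1/0.310 = 3.23. Noncentral t power is 0.884 with the plan's 43 degrees of freedom and 0.885 with 30 + 16 − 2 = 44. Both agree with the claim of over 85%. Simulated Mann-Whitney power is 0.865 normal, 0.871 gamma and 0.833 shifted t, against 0.871, 0.874 and 0.841 in the plan. The gamma figure uses unrounded scales 1/7.89 and 1/8.89. All three agree within simulation error and rounding.

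**Step 2. Power within one gender, if separate tests are meant.** SE = √(1/15 + 1/8) = 0.438 log. The t-test has power 0.587. Simulated Mann-Whitney power is about 0.56 (normal), 0.56 (gamma) and 0.52 (shifted t).

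**Step 3. Discordance with the same 1 log effect in both genders.** The strata are independent, so with p = 0.556:

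- both significant: p² = 0.309
- exactly one significant: 2p(1 − p) = 2 × 0.556 × 0.444 = 0.494
- neither: (1 − p)² = 0.197

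Direct simulation gives 0.308, 0.495 and 0.197. Among trials with a significant pooled test, exactly one gender is significant in 54%. Because 2p(1 − p) peaks at p = 0.5, the design value lies close to the worst point.

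**Step 4. Dependence on the true common difference** (normal data, alpha 0.05):

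| True difference, both genders | Stratum power | Exactly one significant |
|---|---|---|
| 0 log | 0.05 | 9% |
| 0.5 log | 0.18 | 29% |
| 0.75 log | 0.35 | 45% |
| 1 log | 0.55 | 50% |
| 1.25 log | 0.74 | 38% |
| 1.5 log | 0.88 | 21% |
| 2 log | 0.99 | 3% |

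Applying the 0.01 level that Section 9.4.1 sets for secondary endpoints does not cure this: at 1 log, stratum power falls to about 0.28 and discordance is still about 40%.

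**Step 5. How well discordance separates the cases.** With effects of 1 and 1 log, discordance is 50%. With 1.5 and 0.5 log it is 74%, and with 2 and 0 log it is 94%. A one-gender result is therefore weak evidence of modification unless the modification is extreme.

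**Step 6. The direct contrast.** Take the difference between the two gender-specific country effects on log peak titer. SE = √(2 × (1/15 + 1/8)) = 0.619 log, on 46 − 4 = 42 degrees of freedom. The 95% CI half-width is about 1.25 log. Type I error is 5%. Power is 12% for a 0.5 log difference between genders, 35% for 1 log, 66% for 1.5 log and 88% for 2 log; 80% power needs about 1.78 log.

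**Step 7. If one combined test is meant.** A van Elteren test has simulated power of about 0.86 for the country effect and produces no discordant pair of results. It tests a common country effect, so it too is silent on whether that effect differs by gender.

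**The case against.** The sentence on gender is a supportive look in a 46-person mechanistic study. It says only that the matter will be investigated, and a combined stratified rank test is an ordinary reading of stratified. All of that is fair. The 50% figure applies only to the separate-test reading, and only near the design effect.

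Three stronger readings are tempting, and the documents do not support them.

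- A reader might infer that stratifying replaces the pooled test and discards information. It does not: Section 9.1 states one overall null hypothesis for peak titer, Section 9.2 powers 30 versus 16, and the first sentence of Section 9.4.2 plans that comparison.
- A reader might infer that the plan commits to declaring an effect in one sex only. No section contains such a rule. The gap is that nothing prevents that interpretation.
- A reader might infer that split tests will mislead whatever the truth. Step 4 shows otherwise once the country difference is large.

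It is also true that the direct contrast will not settle the question at this sample size. It does have the right error rate, and its interval shows how little the trial can say. A linear contrast also departs from the plan's rank-based approach, which matters if titers fall below the assay limit; the earlier longitudinal assay described in Section 2.2 had a detection limit of 100.

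**Conclusion.** The point stands as a gap in Section 9.4.2: the stated aim concerns effect modification, and no specified analysis estimates it for peak titer. This holds whichever meaning of stratified is intended.

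If separate Mann-Whitney tests are intended, about half of trials would show significance in exactly one gender when gender has no bearing on the difference. That assumes 15 versus 8 per gender, a common 1 log effect, SD 1 log and alpha 0.05. The rate is between roughly 29% and 50% for true differences of 0.5 to 1.25 log, and falls to 3% at 2 log. The primary country comparison and its stated power are not affected. The text should be revised, but the trial's main conclusion does not depend on it.

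**What to change.** In Section 9.4.2:

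- State that the overall country test on all vaccinated participants is the sole primary test, and say explicitly whether it is the plain or the gender-stratified rank form.
- Judge the impact of gender by a country-by-gender contrast on log peak titer: the difference between the gender-specific country effects with a 95% CI, labelled exploratory.
- Name a rank-based or permutation version for use if titers fall below the assay limit. One option is the difference between genders in the probability that a Minnesotan titer exceeds a Ugandan one.
- Show medians and interquartile ranges by country within gender, in line with Section 9.4.1, without separate significance claims.
- State the expected precision: SE about 0.62 log, CI half-width about 1.25 log, and 35% power for a 1 log difference between genders. A non-significant contrast must not be read as absence of a gender effect.

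The cost is a few sentences and one additional model. No further participants, visits or samples are needed. The downside is a wide interval, which reflects what 46 participants can show.

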9.4.3 ANALYSIS OF THE SECONDARY ENDPOINT(S)

Differences in rate of YFV antibody titer decay will be compared between vaccinated Ugandans and Minnesotans using linear mixed effects regression model with measurement time, country, and the interaction between measurement time and country as predictors. Baseline LN measures (area with collagen, area with desmin staining, frequency and size of B cell follicles, and frequency of Tfh cells) will be compared between the two countries using Mann-Whitney U tests.

We will examine the association between vaccine response over time and baseline LN measures using linear mixed effects models adjusting for measurement time and gender.

To examine differences in infection patterns between the two countries, we will perform principal component analyses on the baseline pathseq data. We will test for differences in infection patterns between Uganda and the US populations using logistic regression with country as the outcome and the scores for each of the first five principal components as predictors. Differences in helminth infections between Ugandans and Minnesotans will be compared using Fisher's exact test.

We will examine the association between infection history and baseline LN architecture by fitting separate linear regression models for each measure of baseline LN architecture with gender and the 5 pathseq principal component scores as predictors. The association between helminth infections and baseline LN architecture measures will be assessed using Mann-Whitney U tests.

To elucidate the role of previous infections on inflammation and activation we will use sparse canonical correlation analysis (Reference: Witten, D., Tibshirani, R., & Hastie, T. (2009). A penalized matrix decomposition, with applications to sparse principal components and canonical correlation analysis. *Biostatistics*, 10(3), 515-534.) to identify sets of organismal sequences correlated with baseline measures of systemic and lymphatic inflammation (plasma cytokines, frequency of TGF β + and TNF+ cells in lymphoid tissues) and immune activation (Ki67+ and CD69 + cells). The association between helminth infection and measures of inflammation and activation be assessed using a logistic lasso regression model. Measures which have non-zero coefficients in the model will be considered associated with helminth infection.

The association between change in measures of CD8 function (IFN γ , TNF α , and IL-2) after vaccination and measures of LN architecture will be examined by fitting mixed effects linear models using area with collagen staining, area with desmin staining, and measurement time and gender as predictors.

The association between immune function after vaccination and measures of inflammation and activation will be assessed using separate lasso regression for each measure of immune function (antigen specific CD4, CD8 function measures, and CD4 and CD8 subpopulations). Inflammation and activation measures which have non-zero coefficients in the model will be considered predictive of immune function.

We will examine the impact of measures of immune function on YFV response using separate mixed effects linear models with gender, measurement time and measures of immune function (antigen specific CD4, CD8 functional variables, or CD4 and CD8 subpopulations) as predictors. Similar models will be fit for YF specific IgM, IgG1, IgG2, IgG3 and IgG4 responses.

The impact of vaccination on measures of inflammation and activation be assessed using mixed effects repeated measures model with gender, measurement time, and vaccination status as predictors. To assess the impact of vaccination on CD4 and CD8 cells in LT similar models will be fit, but only gender and vaccination status (measurement taken before or after vaccination) will be used as predictors.

Missing data will not be imputed and a significance level of 0.01 will be used for secondary analyses due to the large number of hypotheses to be tested. The results from all of these investigations will be reported so that the reader can assess the effect of multiple hypothesis testing.

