YFV antibody responses were blunted and of short duration. Titers of neutralizing antibodies to YF were measured by plaque reduction assay (PRA). Initially we compared the week 2 samples between Group 1 and Group 3 using a PRA assay with a lower limit of detection of 10 plaque forming units (pfu) and found only a few of the Ugandans had detectable antibodies whereas most of Group 3 had detectable antibodies ($p < 0.0001$, **Fig. 5A**). We point out that we only had access to plasma samples from Group 3

at the 2 time-points (i.e., D0 and W2) and LN biopsies were not done in that study, so our comparative analysis of antibody formation and decay between these two groups is limited. However, as described below there are historical controls that can be used with Group 1 to make relevant comparisons about peak titer and decay rate(12). We next studied the longitudinally collected plasma samples from Group 1 using a PRA assay with a limit of detection of 100 pfu. We switched to a PRA with a higher threshold of detection titer because the lab performing the first analysis was no longer available to us. We did not duplicate the analysis between Group 1 and 3 as there was limited sample available. Peak titer was seen at the week 3 time-point with a 1.3 log range and a median decrease of 0.9 log by week 60 (Fig. 5B).

These response rates and decay characteristics are similar to those reported by Muyanja in a similar group of Ugandans (12) (and personal communication [name], 2017). Given the variable response in antibody formation and the anatomic changes we found in Ugandan LN, we looked for an anatomic correlate of poor vaccine response and found that measures of the FRCn correlated to the peak antibody titer; the more FRCn, the higher the peak titer of antibodies ($p = 0.02$, Fig. 5C).

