9.4 STATISTICAL ANALYSES

9.4.1 GENERAL APPROACH

Medians and interquartile ranges will be presented for descriptions of continuous data. Percentages will be presented for categorical data.

Counts of cell frequency and QIA endpoints involving the percent area will be log-transformed and linear regression analyses will be conducted where appropriate. If there are no detectable cells or there is no staining detected for a large portion of study participants logistic regression modeling will be conducted, instead, with presence or absence of the measure being the outcome.

Two-sided tests will be conducted for all comparisons. Subjects specific random effects will be included in all mixed effects models and permutation p-values will be presented. To control for multiple comparisons, a cut-off of alpha=0.01 will be used for determining statistical significance of all secondary endpoints.

Measures which have non-zero coefficients in lasso models will be considered to be associated with the outcome. Measures which have non-zero correlation coefficients after applying sparse canonical correlation analysis will be considered to be correlated with the outcome measure.

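### The titer decay model has no rule for values below the assay's detection limit; with a limit near 100 this can bias the country-by-time comparison

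*Combined protocol and SAP*

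**What the plan says.** Section 9.4.3 compares the rate of titer decay between countries with a "linear mixed effects regression model with measurement time, country, and the interaction between measurement time and country as predictors". Section 9.4.1 adds: "Subjects specific random effects will be included in all mixed effects models and permutation p-values will be presented". Secondary endpoints are judged at 0.01 (9.4.1: "a cut-off of alpha=0.01 will be used for determining statistical significance of all secondary endpoints").

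The only rule for undetectable values is in 9.4.1: "If there are no detectable cells or there is no staining detected for a large portion of study participants logistic regression modeling will be conducted". It follows a sentence about cell counts and percent-area image measures, and does not mention titers. Section 9.4.3 says "Missing data will not be imputed and a significance level of 0.01 will be used for secondary analyses", without saying whether a below-limit titer counts as missing.

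Section 2.2 describes two neutralization assays from earlier work. The first had a limit of 10. The longitudinal samples were then run "using a PRA assay with a limit of detection of 100 pfu", with this result: "Peak titer was seen at the week 3 time-point with a 1.3 log range and a median decrease of 0.9 log by week 60". Section 9.2 assumes mean peaks of 7.89 log in Uganda and 8.89 log in Minnesota, each with SD about 1. The plan states neither the log base nor the limit of the assay to be used in this trial.

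**The concern.** A titer recorded at the floor cannot fall further. If one cohort starts lower, more of its members reach the floor, and their recorded slopes are flatter than their true slopes. Section 9.2 assumes that Uganda starts 1 log lower, so the distortion differs by country and enters the country-by-time term directly. Coding at the limit would make Ugandan decay look slower than it is. That could create a difference where none exists, or hide a faster Ugandan decline.

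Permutation p-values do not remove this. The recorded slopes really do differ once one cohort is floored more often, even when the true slopes are equal.

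The models in 9.4.3 that relate vaccine response to lymph node measures and to immune function use the same titers and share the gap. Titers are also scheduled at Day 1 and in the first days after vaccination, in people screened for absence of yellow fever antibody. Section 9.4.3 does not limit the decay model to visits from the peak onward.

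**Working it through.** **The plan's own figure.** Section 9.2 claims over 85% power for a 1 log difference with SD 1, 30 against 16, two-sided 0.05. The noncentrality is 1/√(1/30 + 1/16) = 3.23. With the stated 43 degrees of freedom, power is 0.884, so the claim holds. A Mann-Whitney simulation with normal data gave 0.857 (plan: 0.871). The plan gives no power or error figure for the decay model.

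**Inputs from the documents.** 30 and 16 participants; peak means 7.89 and 8.89, SD 1 (9.2); fall of 0.9 log from Week 3 to Week 60 (2.2); limits of 10 or 100 (2.2); alpha 0.01 (9.4.1).

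**Assumptions, varied because the plan is silent.** Log base; whether the 0.9 fall is in the same base; within-person SD 0.3 or 0.5 within the total SD of 1; titers at Weeks 3, 8 and 78 only, or at all 11 stored-plasma visits from Week 3. True decay is linear and equal in both countries, there is no dropout, and the limit is on the same scale as the means.

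**Share below the limit at Month 18 (Week 78).** The expected fall is 0.9 × 75/57, and the share is Φ(limit − mean at Week 78), since SD is 1.

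Natural log, limit 100, 0.9 log10 fall:
- Fall = 0.9 × 2.303 × 75/57 = 2.73; limit = ln 100 = 4.61.
- Uganda: 7.89 − 2.73 = 5.16; Φ(4.61 − 5.16) = 29%.
- Minnesota: 6.16; Φ(4.61 − 6.16) = 6%.
- If decay also varies between people with a CV of 30%, the shares are 33% and 11%.

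log2, limit 100, 0.9 log2 fall:
- Fall = 0.9 × 75/57 = 1.18; limit = log2 100 = 6.64.
- Uganda: 6.71, 48% below. Minnesota: 7.71, 14-15% below.

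**Simulated country-by-time result with equal true decay, below-limit values set to the limit.** The model was a random-intercept interaction model, with country labels permuted.

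| Reading | Floored at Month 18, Uganda / Minnesota | Apparent slower decay in Uganda (log/year) | False positives at 0.01, permutation | Same, model p-value |
|---|---|---|---|---|
| natural log, limit 100, 0.9 log10 fall | 29% / 6% | 0.08-0.11 | 3-4% | 3-15% |
| log2, limit 100, 0.9 log2 fall | 48% / 15% | 0.16-0.18 | 9-18% | 11-57% |
| log2, limit 100, 0.9 log10 fall | over 95% in both | about 0.7 | 72-79% | 88-98% |
| log2, limit 10, 0.9 log10 fall | 26% / 5% | 0.07-0.10 | 2-4% | 3-8% |
| natural log, limit 10 | under 1% | under 0.01 | about 1% | about 1% |
| natural log throughout, limit 100 | 2% / 0% | under 0.01 | about 1% | about 1% |
| log10 throughout | 0% | under 0.01 | about 1% | about 1% |

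For scale, the true slope in the first row is 0.9 × 2.303 × 52/57 = 1.89 log/year, so the bias is 4-6% of it. In the second row the true slope is 0.82, and the bias is 20-22%. In the first row, the highest model-based rate comes from using all 11 visits with the smaller within-person SD.

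**Other codings.** Half the limit brings the bias close to zero in the first two rows, reverses it in the fourth (−0.04 to −0.06 log/year) and does not cure the third. Dropping below-limit values leaves 0.06-0.10 log/year in the first two rows, with 2-3% false positives.

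**Left-censored (Tobit) random-intercept model, within-person SD 0.5.** With three visits the spurious difference falls from 0.12 to 0.01 log/year (first row) and from 0.17 to −0.02 (second row). With 11 visits it falls from 0.08 to 0.00 and from 0.16 to 0.00. False positives at 0.01 fall from 5-22% to 0.7-2.7%, within simulation error of 1%.

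**The case against.** The strongest reply is that the size rests on quantities the plan does not give. That stands. The limit of 100 belongs to an earlier study that changed assay when a laboratory became unavailable, and several readings give no bias at all. The direction also depends on the coding rule, so it cannot be said outright that the bias runs against the trial's hypothesis.

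A reader might infer three stronger things, and the documents do not support them:

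- **Most trials of this design would give a false positive.** On the stated means, that needs the third row of the table. There, a peak of 7.89 log2 is a titer of about 237, only 0.38 log10 above 100, so a measured median fall of 0.9 log10 could not have been seen when values are coded at the limit. Log10 peaks close to the limit would also give high rates, but no section states such peaks.
- **The Week 2 data show Ugandans at the floor during decay.** Section 2.2 reports few detectable Ugandans at Week 2, but places the peak at Week 3. That sample is pre-peak, and no section reports a participant who never became detectable.
- **Never-detectable people should be left out of the decay comparison.** That would condition on a post-vaccination outcome expected to differ by country, and would depart from 9.3, which includes those who received the vaccine.

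On scope, this is a secondary analysis. A country difference in decay is not among the hypotheses listed in 9.1, although Section 3 expects durability to differ and 9.4.3 plans the test. The primary Mann-Whitney comparison is rank-based and affected only through ties.

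The reading in which all figures are natural logs is less comfortable than it looks. Section 9.2 takes SD 1 from previous work, while 2.2 reports a 1.3 log range. Twenty normal values with SD 1 have an expected range of about 3.7. If 2.2 is in log10, 1.3 becomes 2.99 natural logs, which fits better. The same argument weakens the second row of the table, where one base is used throughout. Truncation at the floor could also have narrowed the range, so this does not settle the base.

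**Conclusion.** The omission is certain: no section handles titers below the detection limit, and 9.4.3 fits an uncensored model to them. The consequence is conditional. If the limit is near 100, the means in 9.2 are natural logs and the fall in 2.2 is log10, the planned permutation test rejects true equality 3-4% of the time instead of 1%. Model p-values do so 3-15% of the time, with Uganda appearing to decay slightly more slowly when values are coded at the limit. On a log2 reading with a 0.9 log2 fall, the permutation rate is 9-18%. At limit 10 on the natural-log scale, or with natural logs throughout, there is no material problem. These rates assume equal linear decay, no dropout and a 1 log difference in peak. The point should be addressed because the result would otherwise turn on an unstated coding choice, and a better method is available at little cost.

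**What to change.** In 9.4.3:

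- Fit all titer models (country-by-time, lymph node measures, immune function) as left-censored (Tobit) mixed models at the assay's detection limit.
- Restrict the decay comparison to visits from the peak onward. Reconcile which visits carry a titer: the Schedule of Activities marks Week 3, which the Section 8.2 text omits, while that text lists Day 17, which the schedule does not mark.
- Keep every vaccinated participant in the models, including anyone never detectable, and report the number never detectable by country as well.
- State one assay, one detection limit and one log scale for both cohorts and all visits.
- Add a sensitivity analysis over substitution values (the limit, half the limit), and say that below-limit titers are not missing data.
- State how permutation p-values will be obtained from the censored model. When peaks differ, floored data are not exchangeable between countries even under equal decay.

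The cost is SAP wording, somewhat wider intervals because floored values are no longer treated as exact, and more computing, chiefly for refitting under permutation. No visit or sample is added.
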